***If F9 is equal to South Africa skip to F9b which province, Else skip to F10.***

***If F9 is equal to Other skip to F9c, Else skip to F10.***

F9b. Which province in South Africa is partner 1 from?

- 1 Eastern Cape
- 2 Free State
- 3 Gauteng
- 4 KwaZulu Natal
- 5 Limpopo
- 6 Mpumalanga
- 7 North West
- 8 Northern Cape
- 9 Western Cape
- 97 Don't Know
- 98 Refuse to answer

F9c. Please specify which country partner 1 is from:

-----

F10a. Do you live with partner 1?

- 1 Yes

2 No

99 Refuse to answer

F10b. Is partner 1 currently working (Choose one)?

1 Yes, self-employed

2 Yes, employed full or part-time

3 No, unemployed **SKIP to F11**

97 Don't know

98 Refuse to Answer

F10c. What type of work is partner 1 doing?

- 0 Mining
- 1 Transport/cargo delivery
- 2 Military/police
- 3 Medical/healthcare
- 4 Business/sales/retail
- 5 Farming
- 6 Teacher/ education/ student
- 7 General labour (domestic worker, gardener, janitorial)
- 8 Civil service (examples including working in government office, post office)
- 9 Other
- 97 Don't Know
- 98 Refuse to Answer

F10d. *If F10c=10 Else SKIP* If Other, What is partner 1's occupation?

---

***If F1a is equal to 1 and F1b is equal to 0, then skip to Section G.***

F12. What is partner 1's HIV status? (Choose one)

- 1 Positive
- 2 Negative
- 3 Unknown
- 98 Refuse to Answer

***If F12 is not equal to 1, skip to F14***

F13a. Does partner 1 take HIV medications? (Choose one)

- 0 No
- 1 Yes
- 97 Don't Know
- 98 Refuse to Answer

F14. Does partner 1 have hepatitis?

- 1 Yes
- 2 No
- 97 Don't Know
- 98 Refused to answer

F15. Did you become sexually involved with partner 1 because you thought that he/she would provide you with some material benefit that you wanted or needed, such as food, shelter, transport, school fees, or other goods?

- 0 No
- 1 Yes
- 97 Don't Know
- 98 Refuse to Answer
- 99 Not Applicable

F15a. If yes, can you tell us what you wanted or needed? It could be food, clothes, transport, school fees, residence, fees, somewhere to stay or sleep, alcohol, drugs, cash or something else.

---

F16. Where did you first meet partner 1? (Choose one)

- 1 Bar, nightclub, restaurant, tavern, shebeen, coffee shop
- 2 Strip club, "Adults Only" club, sex club
- 3 Street, park, library, public transportation, minibus taxi, train
- 4 Party, braai, political function, stokvel or church
- 5 Internet
- 6 Dating service, newspaper ads
- 7 Gym, sports event
- 8 School, technicon, university, college
- 9 Work
- 10 Met some other way
- 97 Don't Know
- 98 Refuse to Answer

***If F16 is not equal to 10, then skip to instruction before F17.***

F16a. Please tell us where you met partner 1:

-----

***If B1 is equal to 1 and F3 is equal to 1, then skip to F19***

F17. Number of times you had vaginal sex with partner 1 in the 6 months before donation. (Choose one)

- none
- 1 to 3 times
- 4 to 10 times
- more than 10 times
- Don't Know
- Refuse to Answer

***If F17 is equal to none, then skip to F19.***

F18. When you had vaginal sex, how frequently did you use condoms? (Choose one)

- never
- some of the times
- every time
- Don't Know
- Refuse to Answer

F19. Number of times you had anal sex with partner 1 in 6 months before your donation? (Choose one)

- none
- 1 to 3 times
- 4 to 10 times
- more than 10 times
- Don't Know
- Refuse to Answer

***If F19 is equal to none, then skip to F25.***

F20. When you had anal sex, how frequently did you use condoms? (Choose one)

- never
- some of the times
- every time
- Don't Know
- Refuse to Answer

***If F3 is equal to 2, then skip to F23.***

F21. Number of times you had insertive anal sex (inserted your penis in partner 1's anus) in the 6 months before your donation? (Choose one)

- none
- 1 to 3 times
- 4 to 10 times
- more than 10 times
- Don't Know
- Refuse to Answer

***If F21 is equal to none, then skip to F24.***

F22. When you had insertive anal sex, how frequently did you use condoms? (Choose one)

- never
- some times
- every time
- Don't Know
- Refuse to Answer

F23. Number of times you had receptive anal sex (partner 1 inserted his penis into your anus) in the past 6 months. (Choose one)

- none
- 1 to 3 times
- 4 to 10 times
- more than 10 times
- Don't Know
- Refuse to Answer

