#### **4. Objectives**

1a: To identify the demographic and behavioural risk factors associated with incident HIV infection (based on “NAT yield” or LAg Avidity testing) among blood donors in South Africa.

Hypotheses: 1) The risk factors for incident HIV in blood donors in South Africa will include a recent change in sexual partner, older male/younger female sexual partnership, a greater number of recent sexual partners, unprotected receptive anal intercourse, and lower socioeconomic status.

1b: To identify the demographic and behavioural risk factors associated with incident HBV infection among blood donors in South Africa identified as “NAT-yields” or concordant serology and NAT positive and anti-HBc negative.

Hypotheses: 1) The risk factors for incident HBV in blood donors in South Africa will include greater number of recent sexual partners, recent scarification/tattoo/body markings, and history of personal contact with an HBV-infected person.

2a: To determine HIV subtype and drug resistance profiles among HIV positive donors with recently acquired infection based on year of donation and site of collection, and examine findings with donor demographics and risk behaviors derived in Objective 1.

Hypotheses: 1) The proportion of donors identified with incident HIV infection containing drug resistance mutations will be positively related to the proportion of HIV-positive individuals receiving anti-retroviral therapy at a population-level in South Africa

2b: To determine HBV genotype profiles among HBV positive donors with recently acquired infection based on year of donation and site of collection, and correlate findings with donor demographics and risk behaviors derived in Objective 1

Hypotheses: 1) Incident HBV infections will show differences in genotypes with genotype E increasing when compared to public health data on prevalent infections.

3: To prospectively characterize the virology, immunology and natural history of incident HIV infection among a cohort of recently infected blood donors and a small group of elite controllers in South Africa.

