The purpose of objective 1a is to identify the demographic and behavioural risk factors associated with incident HIV infection among blood donors in South Africa previously identified as “NAT-yield” and other recently acquired infection based on LAg Avidity testing as compared to controls. The outcome variable is whether or not a blood donor has HIV infection. That is, a binomial variable. The predictor variables believed to be associated with HIV in blood donors will include recent change in sexual partner, older male/younger female sexual partnership, a greater number of recent sexual partners, unprotected receptive anal intercourse, and lower socioeconomic status. Other possible predictor variables, e.g., behavioural variables, will be examined to understand their relationship to whether or not the blood donor has HIV infection. The association between the outcome variable and a predictor variable will be examined using categorical data analysis techniques. Bivariate analysis will be conducted using Chi-square tests. Analyses that include more than one predictor variable will be conducted using multiple logistic regression, which may include interaction terms. In addition, nonparametric modeling will be used when there are multiple predictor variables.

The purpose of objective 1b is to identify the demographic and behavioural risk factors associated with incident HBV infection among blood donors in South Africa previously identified as “NAT-yields” and which are anti-HBc negative. The outcome variable is whether or not blood donor has HBV infection. That is, a binomial variable. The predictor variables believed to be associated with HIV in blood donors will include greater number of recent sexual partners, recent scarification/tattoo/body markings, and history of personal contact with an HBV-infected

person. Other possible predictor variables, e.g., demographic variables, will be examined to understand their relationship to whether or not the blood donor has HBV infection. The association between the outcome variable and predictor variable will be examined using categorical data analysis techniques. Bivariate analysis will be conducted using Chi-square tests. Analyses that include more than one predictor variable will be conducted using multiple logistic regression, which may include interaction terms. In addition, nonparametric modeling will be used when there are multiple predictor variables.

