**If F1 is equal to 0, then skip to instruction Section H.**

F2. How many people did you have sex with in the 6 months before your donation? **(THIS INFORMATION DOES NOT APPEAR TO THE RESPONDEN: This is the seed number for the social matrix (0 up to 5 partners in last six months - persons with more than 5 partners will only be asked about 5 partners).**

— —

- 97 Don't Know
- 98 Refuse to Answer
- 99 Not Applicable

**READ and HEARD:** *Now, we want to ask about the people you have had sex with and your sexual partners. If you had more than five partners in the 6 months before your blood donation, we are only going to ask you about the five most recent people you have had sex with and your sexual partners. Please start with the most recent person you had sex with before your blood donation and then move back in time.*

F3. What is Partner 1's gender?

- 1 Male
- 2 Female
- 3 Transgender
- 97 Don't Know
- 98 Refuse to Answer

F4. How old is partner 1?

— —

- 97 Don't Know
- 98 Refuse to Answer

F5. When did your relationship with partner 1 start? We recognize that you may not remember the exact date and so we are asking that you try to recall the month and the year.

Month \_\_\_\_\_ Year \_\_\_\_\_

- 97 Don't Know
- 98 Refuse to Answer
- 99 Not Applicable

F6a. Are you currently have sex with partner 1?

- 0 No
- 1 Yes
- 97 Don't Know
- 98 Refuse to Answer
- 99 Not Applicable

If F6a = yes, skip to F7

F6b When did your relationship with partner 1 end? We recognize that you may not remember the exact date and so we are asking that you try to recall the month and the year.

Month \_\_\_\_\_ Year \_\_\_\_\_

97 Don't Know

98 Refuse to Answer

99 Not Applicable

F7. What type of partner is partner 1? (Choose one)

1 Primary partner - Your husband, wife, boyfriend or girlfriend

2 Regular partner - Had sex with regularly, but not your primary partner (husband, wife, boyfriend or girlfriend)

3 Casual partner - Had sex more than once but not regularly

4 One time partner - Had sex only once

5 Anonymous partner - Did not know, met for sex, never plan to see again

6 Sex worker - Money or other goods were exchanged for sex

97 Don't Know

98 Refuse to Answer

F8. How would you describe partner 1's race or ethnicity? (Choose one)

- 1 Black
- 2 White
- 3 Coloured
- 4 Asian
- 6 Other
- 97 Don't Know
- 98 Refuse to Answer

F9. What country is partner 1 from?

- 1 South Africa
- 2 Zimbabwe
- 3 Malawi
- 4 Mozambique
- 5 Swaziland
- 6 Botswana
- 7 Lesotho

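### Skip rules in the Appendix 7 partner matrix misroute the position-specific anal-sex items, so the direct item for a named Objective 1a exposure misses receptive-only respondents and is put to men and women with female partners

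*Protocol*

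**What the plan says.** Protocol section 4 (Objectives) lists among the Objective 1a hypotheses "a greater number of recent sexual partners, unprotected receptive anal intercourse, and lower socioeconomic status". Section 4.9 (Analytic Approach) repeats the same exposure as a predictor: "greater number of recent sexual partners, unprotected receptive anal intercourse, and lower socioeconomic status".

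The items that measure it are in Appendix 7, Section F. The item "F3. What is Partner 1's gender" is coded 1 male, 2 female, 3 transgender; B1 records the respondent's gender with the same three codes. The order is F19 (frequency of anal sex with this partner), F20 (condom use in anal sex), F21 and F22 (insertive frequency and condom use), F23 and F24 (receptive frequency and condom use), F25 (oral sex). The printed rules are:

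- Before F17: "If B1 is equal to 1 and F3 is equal to 1, then skip to F19".
- After F19: "If F19 is equal to none, then skip to F25".
- Before F21: "If F3 is equal to 2, then skip to F23".
- After F21: "If F21 is equal to none, then skip to F24".
- After F23: an answer of 0 goes to F25, so F24 is meant to depend on F23.

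The same questions are then repeated for up to four more partners.

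**The concern.** Two rules look wrong. The jump after F21 lands one item too far: someone who reports no insertive sex is taken over the receptive-frequency question to the question on condom use during receptive sex. The rule before F21 uses the partner's gender alone, so it treats a man and a woman with a female partner alike, and no rule keeps women with male partners away from F21.

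At stake is one named HIV exposure. If the analysis takes F23 as its direct measure, it is blank by design for respondents whose anal sex was only receptive, and it can pick up spurious positives from men with female partners. The interview is self-administered and private, so staff would not normally see or correct the path. An item that was not asked cannot be collected afterwards.

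**Working it through.** No sample size or power figure is involved. The check is to follow the printed rules for each type of respondent who reports some anal sex at F19, assuming every item is answered accurately, and then to repeat it with the routing given under the fix.

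| Respondent, partner (position) | Asked as printed | Asked with corrected routing |
|---|---|---|
| Man, man (receptive only) | F19, F20, F21, F24, F25 | F19, F20, F21, F23, F24, F25 |
| Man, man (insertive only) | F19, F20, F21, F22, F23, F25 | unchanged |
| Man, man (both) | F19, F20, F21, F22, F23, F24, F25 | unchanged |
| Woman, man (receptive) | F19, F20, F21, F24, F25 | F19, F20, F23, F24, F25 |
| Man, woman (insertive) | F19, F20, F23, F25 | F19, F20, F21, F22, F25 |
| Woman, woman | F19, F20, F23, F25 | F19, F20, F25 |

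Reading the table:

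1. Four of the six types are misrouted. Men with male partners who report any insertive sex are routed correctly.
2. Both receptive-only types miss F23. For women with male partners, the accurate answer to F21 is the one that triggers the wrong jump. Any other answer, including don't know or refused, leads on to F22 and F23, so women may split across two paths.
3. Men with female partners miss F21-F22 and get F23, whose wording presupposes a partner with a penis. Women with female partners get F23 too.
4. Internal evidence shows an error and not a preference. The rule after F23 makes F24 conditional on F23, which fails if F24 can be reached without F23. The rule before F17 already combines B1 and F3, so both genders were available for routing.

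Two smaller mismatches sit in the same block. The rule after F23 tests for 0 while the printed option is none. F23 refers to the past six months, whereas F19 and F21 refer to the six months before the donation.

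How many respondents are affected cannot be computed, because the documents do not say how many donors report anal sex. Table 3 shows that 174 of 300 HIV NAT-only donors (58.0%) were women, so the group routed past F23 is not confined to a minority of men.

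**The case against.** The strongest reply is that the exposure can still be derived. F19 has the same frequency categories as F23, and F20 gives condom use. For a woman with a male partner, the anal sex reported at F19 is receptive. For a man with a male partner who answers none at F21, all of it is receptive, and he still receives F24. A positive F23 from a man with a female partner can be identified from B1 and F3, and section 4.9 plans checks of logical consistency before modelling. This stands, and it limits the consequence. It does not make the rules right: the derivation works only if someone notices the fault and overrides the direct item, and inference from gender is not available where either person is transgender or a gender is not given.

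A reader might infer three stronger things that the documents do not support.

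- That receptive frequency goes unmeasured. F19 and F20 contradict this.
- That men with female partners are offered only a receptive item. They have just answered F19 and F20, and F23 includes a none option.
- That the odds ratio is diluted by a known amount. With assumed exposure of 2% in controls and 5.8% in cases (odds ratio 3.02), and observed prevalence = p + (1 - p) x false-positive rate, rates of 0.5%, 1% and 2% give 2.62, 2.35 and 2.02. That applies the false positives to every unexposed participant, whereas for this exposure only misrouted men could supply them. Taking 42% men (Table 3) and assuming that 5-10% of them report anal sex with a woman, 2.1-4.2% of participants are misrouted in this way. An overall rate of 2% would then need 0.02/0.042 = 48% to 0.02/0.021 = 95% of those men to answer falsely; 1% would need 24-48%, and 0.5% would need 12-24%. The result also assumes an analysis of F23 that ignores partner gender.

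It may also be said that Appendix 7 is plainly a draft: it still carries open drafting queries and placeholder approval numbers, and section 4.11 schedules pilot testing. That explains the slip, but these are the rules as printed.

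**Conclusion.** The point holds as a routing fault in the printed instrument. F23 is structurally missing for receptive-only men with male partners and for women with male partners who answer F21 accurately. It is put to men and women with female partners, to whom it cannot apply, and it is open to spurious answers from those men. Because it is the direct item for a named Objective 1a hypothesis and predictor, it deserves correction and not just proofreading.

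Its size is moderate: four of six traced types, in each of up to five partner loops, with much of the exposure recoverable from F19, F20, F24, B1 and F3. No dilution of the odds ratio can be quantified. The conclusion rests on the skip rules being programmed as printed, with no further gender condition in the ACASI software.

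**What to change.** Before the ACASI is programmed, and in all five partner loops, replace the rules after F20 with routing on both genders:

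- B1=2 and F3=1: skip F21-F22 and go to F23.
- B1=1 and F3=2: ask F21, and F22 if F21 is not none, then go to F25.
- B1=2 and F3=2: go from F20 to F25.
- B1=1 and F3=1: ask F21, and send none to F23, not F24.
- Either gender transgender, don't know or refused: ask both F21 and F23.

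Make the rule after F23 test the printed option none instead of 0, and give F23 the same pre-donation window as F21.

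The cost is a few skip-rule edits and a test of each path during the planned pilot. For the types traced, no path grows by more than one item per partner, and the path for women with female partners is one item shorter. If the instrument has already gone for the approvals named in section 4.6, the corrected routing should be submitted with it. If any interviews have used the printed rules, derive the exposure for them from F19, F20, F24, B1 and F3, and document that derivation.

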***If F23 is equal to 0, then skip to F25.***

F24. When you had receptive anal sex, how frequently did you use condoms? (Choose one)

- never
- some times
- every time
- Don't Know
- Refuse to Answer

F25. Number of times you had oral sex with partner 1 in past 6 months

- none
- 1 to 3 times
- 4 to 10 times
- more than 10 times
- Don't Know
- Refuse to Answer

***Sexual Matrix is completed with same questions for up to 4 additional sexual partners.***

***READ and HEARD: The next set of questions is about your SECOND sexual partner, BEFORE your blood donation.***

***READ and HEARD: The next set of questions is about your THIRD sexual partner, BEFORE your blood donation.***

***READ and HEARD: The next set of questions is about your FOURTH sexual partner, BEFORE your blood donation.***

***READ and HEARD: The next set of questions is about your FIFTH sexual partner, BEFORE your blood donation.***

**SECTION G - SEXUAL PARTNER RISKS**

*If E2a is equal to 0 and E3a is equal to 0 and B1 is equal to 1, then skip to Section H.*

*If E2a is equal to 0 and E3a is equal to 0 and B1 is equal to 2, then skip to Section H.*

**READ and HEARD:** Now, we want to ask about some of the behaviors of the people you have had sex with and your sexual partners. As before when answering, please consider only the following activities, whether or not a condom or other protection was used:

1. *Vaginal sex (contact between penis and vagina)*
2. *Oral sex (mouth or tongue on someone's vagina, penis, or anus)*
3. *Anal sex (contact between penis and anus)*

**You may not know the answers to these questions. Please answer these questions to the best of your knowledge. Several of the questions refer to the period of time in the "six months before your blood donation". This means before your most recent blood donation.**

G1a. To the best of your knowledge, have you ever had sex with anyone who was an injection drug user? (Choose one)

- |    |                  |                    |
|----|------------------|--------------------|
| 0  | No               | Skip to G2a |
| 1  | Yes              |                    |
| 97 | Don't Know       |                    |
| 98 | Refuse to Answer |                    |

G1b. In the 6 months before your donation, have you had sex with anyone who was an injection drug user? (Choose one)

- |    |                  |
|----|------------------|
| 0  | No               |
| 1  | Yes              |
| 97 | Don't Know       |
| 98 | Refuse to Answer |

G2a. To the best of your knowledge, have you ever had sex with anyone who tested positive for HIV? (Choose one)

- 0 No **Skip to instruction before G4a**
- 1 Yes
- 97 Don't Know
- 98 Refuse to Answer

G2b. In the 6 months before your donation, have you had sex with anyone who tested positive for HIV? (Choose one)

- 0 No
- 1 Yes
- 97 Don't Know
- 98 Refuse to Answer

G3a. To the best of your knowledge, have you ever had sex with a man who has had sex with another man? (Choose one)

- 0 No **Skip to G4a**
- 1 Yes
- 97 Don't Know
- 98 Refuse to Answer

G3b. In the 6 months before your donation, have you had sex with a man who has had sex with another man? (Choose one)

- 0 No
- 1 Yes

97 Don't Know

98 Refuse to Answer

G4a. To the best of your knowledge, have you ever had sex with anyone who received a blood transfusion? (Choose one)

0 No **Skip to G5a**

1 Yes

97 Don't Know

98 Refuse to Answer

G4b. In the 6 months before your donation, have you had sex with anyone who received a blood transfusion? (Choose one)

0 No

1 Yes

97 Don't Know

98 Refuse to Answer

G5a. To the best of your knowledge, have you ever had sex with a person with haemophilia? (Choose one)

0 No **Skip to G6a**

1 Yes

97 Don't Know

98 Refuse to Answer

G5b. In the 6 months before your donation, have you had sex with a person with haemophilia?  
(Choose one)

- 0 No
- 1 Yes
- 97 Don't Know
- 98 Refuse to Answer

G6a. To the best of your knowledge, have you ever had sex with anyone who has spent three or more nights in jail, prison, or a detention centre? (Choose one)

- 0 No **Skip to G7a**
- 1 Yes
- 97 Don't Know
- 98 Refuse to Answer

G6b. In the 6 months before your donation, have you had sex with anyone who has spent three or more nights in jail, prison, or a detention centre? (Choose one)

- 0 No
- 1 Yes
- 97 Don't Know
- 98 Refuse to Answer

G7a. To the best of your knowledge, have you ever had sex with anyone who had a job that involved exposure to human blood or other body fluids? (Choose one)

0 No ***Skip to Section H***

1 Yes

97 Don't Know

98 Refuse to Answer

G7b. In the 6 months before your donation, have you had sex with anyone who has a job that involves exposure to human blood or other body fluids? (Choose one)

0 No

1 Yes

97 Don't Know

98 Refuse to Answer

